5.4 Subject data protection

The ICF includes information that data generated during the investigation will be recorded, collected and processed and may be transferred to countries within the European Economic Area (EEA). In accordance with the General Data Protection Regulation 2016/679 (GDPR), the data will not identify any persons taking part in the investigation.

The potential investigational subject should be informed that by signing the ICF he/she approves that authorized representatives from the Sponsor and sponsor representatives (i.e CRO), the IEC and the Competent Authorities, as applicable, have direct access to his/her medical records for verification of clinical investigational procedures.

To ensure the confidentiality of the subjects in the clinical investigation each subject will receive a pseudonymised subject ID within the database. The subject identification list will be kept separately by the site in a secure manner. The Investigator must file a subject identification list, which includes sufficient information to link records, i.e. the CRF and clinical records. This list should be preserved for possible future inspections/audits but should not be made available to the Sponsor or sponsor representatives except for monitoring or auditing purposes.

Document	Doc. id.	Version	Page
Clinical investigation Plan / Investigation code- AI-DSMM/	GR 21- 023	01	16 (52)

All data going to and from Trial Online are secured using strong encryption. It is not possible to gain access to data being transmitted from the web browser. The databases comprising the system are located in a secure data centre with strong physical protection in place. Access to the servers is protected by using strong authentication (individual username and password combination as well as a one-time password). Data is backed up every 24 hours and all backup data is backed-up once every 24 hours to a separate data centre facility. Access to infrastructure elements and backup copies is limited and controlled. User access will be checked and followed up on a regular basis during the investigation.

5.5 Risks and benefits of the Investigational Medical Device and clinical investigation

5.5.1 Risks/benefit associated with participation in the clinical investigation

There are no foreseen risks to participate in the clinical investigation than those according to current standard of care for the target population. The IMD is a software and not in contact with or used by the subjects. The subjects will receive the same standard of care as they would if they were not participating in the clinical investigation. The outcome of the IMD AI will not influence the treatment of the subject. The IMD log-in screen is marked "use only for clinical investigation" to ensure it will only be used by investigators participating in the clinical investigation.

5.5.2 Contraindications

It is not recommended analyzing lesions in the following situations.

- Cutaneous lesions masked by an excessive amount of hair.
- Any form of body modification by injecting ink, dyes, and/or pigments covering or surrounding skin lesions.
- Any form of scarring of tissue due to injury.
- Damaged or injured non-intact skin with lesions.
- Cutaneous lesions on non-human subjects.

5.5.3 Risk-to-benefit rationale

There are no additional risks for participating subjects as they will receive the standard of care as per routine at the investigations site. The only added procedure is an additional photo taken for the evaluation by the AI. The healthcare personnel in the investigation will have to perform additional

Document	Doc. id.	Version	Page	
Clinical investigation Plan / Investigation code- AI-DSMM/	GR 21- 023	01	17 (52)	

documentation and answer if the device may be of benefit if applied as diagnostic support after CE-mark. Thus, there are no or low risks and possible benefits, thus the ratio is favourable.

7 INTRODUCTION

Dermalyzer is an Artificial Intelligence (AI) application (app) that allows medical professionals to take pictures of cutaneous lesions with the help of a smartphone camera. A dermatoscope is connected to the smartphone camera and is used to take the digital image of cutaneous lesions with suspicion of melanoma. Based on image processing algorithms, the app does a detailed analysis of the captured cutaneous lesion. Dermalyzer provides information for medical professionals as decision support when assessing skin lesions such as melanoma. The input from the device is not intended to be used as sole information for diagnosis. The software application can be used on either a mobile or a computer.

Dermalyzer is a Medical Device that is not CE-market yet, the plan is to collect clinical data in the planned Clinical Investigation. In the clinical investigation, the technically verified and validated MDSW version 0.0.2 dated 2022 will be applied.

The aim of the current clinical investigation is to determine the diagnostic accuracy of the Dermalyzer device. This medical device investigation has been initiated by the investigators, thus the Sponsor and Investigator is the same under these circumstances.

7.1 Background

Malignant melanoma is a type of tumor resulting from an uncontrolled proliferation of melanocytes (pigment-producing cells), a type of cell found in the mucous membranes, eyes, and innermost layers of tissue covering the brain and spinal cord^{1,2}. Despite advances in both diagnosis and treatment of malignant melanoma, the disease is still a major challenge within healthcare¹. The incidence of the disease among several fair-skinned populations has increased with as much as 4-6 percent yearly^{1,3} and melanoma is one of the cancer types with the highest average years of life lost per death (15 years), so-called AYLL⁴. Melanoma accounts for only 5 percent of cutaneous malignancies, but can be attributed to most skin cancer deaths¹.

During 2020 it was estimated that Europe had a total incidence of approximately 150,000 and the total number of deaths caused by melanoma was approximately 26,000. North America had a total incidence of approximately 105,000 and the total number of deaths caused by melanoma was approximately 8,500. Oceania had a total incidence of approximately 19,000 and the total number of deaths caused by melanoma was approximately 2000⁵.

Document	Doc. id.	Version	Page	
Clinical investigation Plan / Investigation code- AI-DSMM/	GR 21- 023	01	20 (52)	

Primary care and general practitioners play a vital role in detecting patients with suspected skin lesions and thus in detecting melanoma at early stages⁶. Histopathology (or 'Pathologic anatomic diagnosis', PAD) is considered the gold standard in melanoma diagnosis. For histopathological diagnosis the suspected lesion is excised and inspected by a dermatopathologist, who can report on characteristics, such as melanoma subtype, tumor thickness and ulceration. If the malignancy is not detected at an early stage and is allowed to metastasize and spread outside its primary location, it is more challenging to treat and the chance of survival decreases¹. If detected at an early stage, excision of the skin lesion is associated with a high chance of survival⁷. On the other hand, unnecessary excision of benign skin lesions are common and leads to increased morbidity as well as increased healthcare costs⁸. The direct and indirect healthcare and societal costs for diagnosing and treating malignant melanoma, as well as costs associated to melanoma deaths, are significant ^{1,8}.

Detection and treatment of melanoma in early stages takes up only a fraction of the resources needed to treat melanoma in later stages. Early detection can thus contribute to cost savings⁷. Innovative technological solutions used in secondary preventive strategies have the potential to reduce costs^{1,7}. Although significant progress has been made in recent years, much more research and innovation are needed³. Given the severity of the disease, in terms of rising incidence and mortality rates and the associated costs, it is important to develop cost-effective methods to facilitate skin lesion examinations. Diagnosis of melanoma in early stages is in the best interest to patients, payers and the healthcare system⁷.

Artificial intelligence (AI) has, in controlled experimental environments, shown promising results in diagnosing malignant melanoma⁹. Areas such as medical image analysis have almost completely shifted digital images¹⁰. In turn, and in conjunction with AI, enabling physicians to perform faster and more accurate image interpretation¹¹.

Technological advances have also made it possible to implement AI, with significant potential for improving healthcare systems and processes^{12,13}. These technological advances have enabled opportunities for improving healthcare instruments such as diagnostic decision support systems (DDSS)¹⁴. Through decision support systems, AI can partially alleviate and overcome digitalization challenges in healthcare.

7.2 Investigational Medical Device

The Investigational Medical Device (IMD) is Dermalyzer, an Artificial Intelligence (AI) application (app) that allows medical professionals to take pictures of cutaneous lesions with the help of a smartphone camera. A dermatoscope is connected to the smartphone camera and is used to take

Template Doc. id. Version

CIP Template QMS 12-01- 02

01

Document	Doc. id.	Version	Page	
Clinical investigation Plan / Investigation code- AI-DSMM/	GR 21- 023	01	21 (52)	

the digital image of cutaneous lesions with suspicion of melanoma. Based on image processing algorithms, the app does a detailed analysis of the captured cutaneous lesion. Dermalyzer provides information for medical professionals as decision support when assessing cutaneous lesions such as melanoma. The input from the device is not intended to be used as sole information for diagnosis. The medical software (MDSW) application can be used on either a mobile or a computer.

A more detailed description is given in Section 9.4

7.3 Clinical experience

The AI has been trained by batches of photos collected during clinical use of dermoscopes. Several experienced clinicians have been part of the device development. This is the first time the device is tested in clinical settings.

7.4 Rationale for the investigation

There is a clear benefit at group level if the methodology can contribute to safer, more accurate and efficient diagnostic procedures of patients seeking primary care for skin lesions of concern, while there are, on the other hand, no significant risks associated with the study. Potentially fewer cases of unnecessarily excised benign skin lesions would contribute to improved access to care for those with malignant lesions, thereby also increasing the prerequisites for early cancer detection. Overall, the benefits of the study are clearly considered to outweigh the risk(s).

8 INVESTIGATIONAL OBJECTIVES AND ENDPOINTS

8.1 Primary objective

The primary objective of the investigation is to determine the diagnostic precision of the device; to answer at which level the AI tool Dermalyzer can identify malignant melanomas among cutaneous lesions that are assessed in clinical use due to any degree of malignancy suspicion.

Template Doc. id. Version

02

Document	Doc. id.	Version	Page	
Clinical investigation Plan / Investigation code- AI-DSMM/	GR 21- 023	01	22 (52)	

8.1.1 Primary endpoint

The primary endpoint will be measured as the true proportion; by testing if the device based on artificial intelligence (AI) gives correct results as compared with the result of the lesion analysis (the final classification by PAD) in at least a certain proportion (π) of the analyses.

8.2 Secondary objectives

As secondary objectives a number of analyses will be done.

To evaluate usability and applicability in clinical praxis of Dermalytics by users (medical professionals).

To gain an increased knowledge and understanding of how digital tools enhanced co-artificial intelligence can assist physicians with the right support for an earlier diagnosis of malignant melanoma.

8.2.1 Secondary endpoints

User questions including System Usability Scale to evaluate the usability and applicability in clinical praxis.

8.3 Exploratory objectives

To explore health economic aspects of improved diagnosis support.

8.3.1 Exploratory endpoints

Collecting health economic related information by survey to participating sites.

9 INVESTIGATIONAL PLAN

9.1 Overall investigational design and schedule of events

The subjects will be included from primary care centres. If the subject's lesion(s) is suspected of melanoma or melanoma cannot be ruled out the subject is asked to participate in the investigation. The investigator examines the subject's lesion(s) (with or without a dermatoscope) and may also take dermoscopy images according to standard of care. The investigator then makes his clinical

Document	Doc. id.	Version	Page	
Clinical investigation Plan / Investigation code- AI-DSMM/	GR 21- 023	01	23 (52)	_

assessment of the subject lesion(s) based on established clinical decision algorithms (such as "Chaos and clues", "3- or 7-point checklist", or the ABCDE criteria) of whether there is a suspicion of melanoma, according to the usual clinical routine (also includes very low suspicion that cannot be completely dismissed). The investigator decides on action based on his or her MM suspicion (excision at the primary care centre or referral for excision or referral to a dermatologist for further assessment), see figure 1.

If the subject has agreed to participate in the investigation, the investigator indicates in the eCRF his clinical suspicion level of MM and decided action.

The investigator takes images of the lesion(s) again, this time with a mobile phone, containing the IMD AI SW, connected to a dermatoscope, and follows the on-screen instructions, see appendix 13.3. The image is processed by the AI SW and the results are visible on the screen within seconds. A unique auto generated code number is also presented. The code number is registered on the enrollment log and in the eCRF. The investigator records how he considers that the degree of suspicion of MM (higher vs lower) would have been affected by the AI SW result if it had been the governing body for the treatment. When the PAD result is available the outcome is documented in the eCRF.

Figure 1. Investigator workflow for assessing MM suspicion and action to be taken

[figure not shown]

02

AI MEDICAL TECHNOLOGY AIM AB

Document Doc. id. Version Page

Clinical investigation Plan / Investigation code- AI-DSMM/ GR 21- 023 01 24 (52)

Visits and assessments will be performed as described in Table 9.1. Each assessment is further described in Section 9.5.

DocumentDoc. id.VersionPageClinical investigation Plan / Investigation code- AI-DSMM/GR 21- 0230125 (52)

Table 9.1 Schedule of events

	Baseline/ Visit 1	Follow-up 1	Follow-up 2
	Day 1	Day 30(+/-30)	After at least 10 subjects
Informed consent + photo consent	х		
Inclusion/Exclusion criteria	х		
Demographics (Age, melanoma history/family history, race)	х		
Fitzpatrick skin type (exclude V-VI	х		
Lesion assessment (body area, number of lesions, size)	х		
Clinical assessment (naked-eye examination, with or without dermoscopy,) "Chaos&clues", 3-point checklist, ABCDE criteria	х		
Al photo	х		
Histopathology (PAD)		х	
In theory if degree of suspicion affected by device	х		
User questionnaire			x ¹
Health economic outcomes			X ²
Adverse Event	х	x (from journal if relevant)	

[figure not shown]

Document	Doc. id.	Version	Page	
Clinical investigation Plan / Investigation code- AI-DSMM/	GR 21- 023	01	26 (52)	_

¹To be answered by Investigators at one occasion only

Figure 2. Overview of workflow

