The investigator examines the subject's lesion(s) and makes the clinical assessment of the subject lesion(s) based on established clinical decision algorithms (such as "Chaos & clues", "3- or 7-point checklist", or the ABCDE concept) of whether there is a suspicion of MM, according to the usual clinical routine (also includes very low suspicion of MM but cannot be completely dismissed). The investigator takes dermoscopy images according to standard of care and archives the image(s) according to clinical routine. The investigator decides on action, based on his or her MM suspicion (excision at the primary care centre or referral for excision or referral to a dermatologist for further

Template Doc. id. Version

02

Document	Doc. id.	Version	Page	
Clinical investigation Plan / Investigation code- AI-DSMM/	GR 21- 023	01	11 (52)	_

assessment). If the subject has agreed to participate in the investigation, the investigator indicates in the CRF the clinical suspicion level of MM, and decided action.

The investigator takes images of the lesion(s) again, this time with a mobile phone, containing the IMD AI SW, connected to a dermatoscope, and follows the on-screen instructions. The image is processed by the AI SW and the results are visible on the screen within seconds. A unique auto generated code number is also presented. The code number is registered on the enrollment log and in the CRF. The investigator records how he considers that the degree of suspicion of MM (higher vs lower) would have been affected by the AI SW result if it had been the governing body for the treatment.

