When the subject has been fully examined and receives the final tumor diagnosis from the histopathology/PAD results (melanoma/non melanoma), the degree of agreement between the PAD and the outcome of the AI SW decision support is calculated with the Kappa-analysis and the diagnostic accuracy to be able to distinguish melanoma from non-melanoma in the form of sensitivity and specificity as well the positive and predictive value. The corresponding comparison is performed from the examining investigators' estimated clinical degree of suspicion, as well as the diagnostic accuracy when both the PAD and the AI decision support are weighted together (i.e. in cases where the investigator and the decision support are in agreement in their assessment). The clinical investigation will collect information from the users, how participating users (investigators at the site) experience the usability of the AI SW decision support and attaching applications, from short surveys including the validated System Usability Scale.

Use the same overall description given in Section 9.1.

Duration of exposure to the Investigational Medical Device

The subjects will not be in any direct contact with IMD Dermalyzer.

Duration of subjects' involvement in the investigation

The subjects will only perform 1 visit at a primary care centre to assess the cutaneous lesion(s).

Clinical performance assessments

The subject will be examined according to clinical routine. The cutaneous lesions where MM cannot be ruled out (study lesions) will be photographed with a digital dermatoscope. The digital image will then be able to be instantly uploaded to the study's AI enhanced web application (Dermalyzer), where the AI algorithm performs the image analysis within a few seconds.

Template Doc. id. Version

02

CIP Template QMS 12-01-

Document	Doc. id.	Version	Page
Clinical investigation Plan / Investigation code- AI-DSMM/	GR 21- 023	01	12 (52)

Clinical safety assessments

All considered reportable events in accordance with MDR, will be captured. The subject included in the investigation will follow the standard of care. The use of the AI will not influence the subject or the medical care of the subject.

Statistical methods

The sample size of at least eligible 239 lesions is calculated by an expected true proportion of 95% with 80% power. The estimated frequency of actual found malignant melanoma is 4.65% (or 12 MM out of 239 lesions).

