9.4.10 Blinding

The Investigators will have to document their assessment of the included lesion(s) in the eCRF before taking the IMD image in order not to be influenced by the IMD result. When the outcome of the IMD AI result is available the Investigator will evaluate if his/her decision would have changed if taking the result of the AI into consideration.

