9.5.2 Clinical performance assessments

9.5.2.1 Assessment 1

Dermoscopy image with mobile phone and attached dermatoscope

9.5.2.2 Assessment 2

The method applied according to standard of care at each site (Chaos & clues", "3- or 7-point checklist", ABCDE concept or other) for the investigator to make his/hers clinical assessment of the subjects lesions to establish whether there is a suspension of MM will be documented in the CRF.

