The set expectation of 95% true proportion is based on in-silico experiments on a proprietary dataset of images which found a sensitivity of 95.1 \pm 0.6%.

The accuracy of AI decision support will be measured against gold standard (PAD) as well as against experienced dermatologists and general practitioners (average) and verified at: sensitivity> 95%, specificity> 75%, numbers needed to excise (NNE) <7, positive predictive value (PPV))> 15% and negative predictive value (NPV)> 99.5%. The average sensitivity for general practitioners in previous meta-analyzes is estimated at about 81%.

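### The AI versus investigator comparison mixes algorithm with instrument wherever the clinical rating was made without a dermatoscope, and the plan neither names dermatoscope use as a recorded item nor splits by it

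*Combined protocol and SAP*

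**What the plan says.** **Clinician's input.** Section 9.1 states: "The investigator examines the subject's lesion(s) (with or without a dermatoscope) and may also take dermoscopy images according to standard of care". Table 9.1 lists the Day 1 item as "Clinical assessment (naked-eye examination, with or without dermoscopy". Both leave dermoscopy optional. The synopsis (Methodology) is worded differently: "The investigator takes dermoscopy images according to standard of care and archives the image(s) according to clinical routine".

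**AI's input.** Section 9.1: "The investigator takes images of the lesion(s) again, this time with a mobile phone, containing the IMD AI SW, connected to a dermatoscope". Section 9.4.9 names the dermatoscope models to be attached.

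**Order.** Section 9.4.10: "The Investigators will have to document their assessment of the included lesion(s) in the eCRF before taking the IMD image". After seeing the AI output, the investigator records how it would have shifted the suspicion of melanoma.

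**Comparison.** The synopsis sets out kappa, sensitivity, specificity and predictive values for the AI against PAD, and adds: "The corresponding comparison is performed from the examining investigators' estimated clinical degree of suspicion". Section 9.7.6 also says AI accuracy is to be measured against PAD "as well as against experienced dermatologists and general practitioners (average").

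**Recording.** Section 9.5.2.2 puts in the CRF "The method applied according to standard of care at each site", with decision algorithms as the examples. It does not name dermatoscope use as an item.

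**The concern.** The two sides of the comparison may not see the same information. The AI always has a dermoscopic image, whereas the investigator may have rated by eye alone. In those lesions, any AI advantage or disadvantage is that of the algorithm and the instrument together.

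The item on changed suspicion has a related problem. An investigator who rated by eye then handles the dermatoscope to take the AI image and sees the AI result seconds later, with no rating in between. Part of a reported shift could come from the dermoscopic view.

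At stake is what the study can say about its secondary objective in section 8.2, how such tools assist physicians. The device needs a dermatoscope, so a natural question is what the AI adds for a physician already using one. Without a record of who rated with one, the data may not answer that.

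**Working it through.** **1. What the planned sample size rests on.** Table 2 gives 239 lesions for a rejected proportion of 90%, a true proportion of 95%, a one-sided 2.5% level and 80% power:

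n = [(1.960·√(0.90·0.10) + 0.842·√(0.95·0.05)) / 0.05]² = [(0.5880 + 0.1834) / 0.05]² = 238.03, rounded up to 239.

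Under the exact binomial test at n = 239, success needs 225 or more correct, with a one-sided level of 0.0162 and power 0.781. The figure reproduces. It uses only AI against PAD, so the investigator's rating and how it was made do not enter.

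**2. Inputs side by side.**

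| | Investigator's rating | AI result |
|---|---|---|
| Dermoscopic information | Optional (9.1, Table 9.1) | Always (9.1, 9.4.9) |
| Timing | Recorded before the AI image (9.4.10) | After the rating |
| Reference | PAD | PAD |
| Split by dermoscopy use | None stated | Not applicable |

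Because the rating is recorded first, a lesion rated by eye never receives a dermoscopic rating free of the AI result.

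**3. Size of the instrument component.** Take one accuracy measure, for example sensitivity. Let q be the share of the relevant lesions rated by eye, and d the gain those ratings would have had from a dermatoscope. Then:

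AI − investigator as rated = (AI − investigator with a dermatoscope throughout) + q × d.

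The documents give neither q nor d. The values below are assumptions, in percentage points:

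| q | d = 5 | d = 20 |
|---|---|---|
| 0% | 0 | 0 |
| 25% | 1.25 | 5 |
| 50% | 2.5 | 10 |
| 100% | 5 | 20 |

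This illustrates one component, with its sign assumed. It is not an estimate of the net bias.

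**4. Precision of a split.** Section 9.3.2 requires at least 12 melanomas. Exact 95% intervals for sensitivity with 12:

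- 10/12 detected: 51.6% to 97.9%
- 11/12 detected: 61.5% to 99.8%
- 12/12 detected: 73.5% to 100%

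When all n are detected, the lower limit is 0.025^(1/n). For n = 12 it is 0.735. If the melanomas divided evenly between strata (assumed), n = 6 gives 0.541 even with perfect detection.

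**The case against.** **No decision rests on this comparison.** The primary endpoint is AI against PAD, and the only named secondary endpoint is usability. The comparison has no hypothesis or success rule. The numeric targets in 9.7.6 are fixed AI thresholds, not differences from the study's investigators. This stands and limits the weight of the point.

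**Usual care is a coherent comparator.** Section 9.2 justifies a design that leaves care unchanged, and the device is used with a dermatoscope. Dermatoscope plus AI against usual assessment is a valid contrast. This also stands: the all-lesion figure should be kept and labelled for what it is.

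**Absence of a split is not proven.** Section 9.7.3.2 defers further analyses to an SAP, and no separate SAP text is included in the combined document. The CRF may already hold the field. If so, the protocol only needs to say so.

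**The synopsis may not conflict much with 9.1.** A reader might infer that the synopsis requires dermoscopy for every rating. It does not say that. It refers to standard of care, mentions the images after the clinical assessment, and taking an archive image is not the same as rating with a dermatoscope. Both texts speak of taking images again, which suggests earlier images are expected, so the naked-eye share could be small. The wordings still differ, although a note in the synopsis asks for the same description as 9.1.

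**A split does not isolate the algorithm.** Dermatoscope use is not randomised and may follow site, skill or lesion difficulty. This is a reason to report the strata descriptively, not to omit them.

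**Conclusion.** The point holds as a low-cost improvement. As written, the comparison cannot separate the AI's contribution from the dermatoscope's in lesions rated by eye, and the change-in-suspicion item may be partly confounded there.

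A reader might infer that the comparison favours the AI by some definite amount. The documents do not support that. Both the naked-eye share and the gain from dermoscopy are unknown, and the component vanishes if all ratings used a dermatoscope. Its sign assumes dermoscopy helps on the measure in question. Selection could also work the other way: lesions the investigator judges benign are excluded (9.3.5), so every enrolled lesion already carries some suspicion, which can raise the investigator's sensitivity.

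Nor does it follow that a shift in suspicion can never be credited to the AI. The item asks about the AI result specifically, and the problem is limited to lesions not previously viewed by dermoscopy.

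**What to change.** - **Record.** Add to 9.5.2.2 a required yes/no field per lesion, completed before the AI image, for whether a dermatoscope was used for the clinical rating.
- **Report.** Give the AI versus investigator comparison and the change in suspicion for all lesions, labelled as dermatoscope plus AI versus usual assessment. Give both again by dermoscopy use, descriptively, with exact confidence intervals and a note that the strata are not randomised.
- **Interpret.** Base any statement about what the AI adds for a physician using a dermatoscope on the dermoscopy-rated lesions.
- **Reconcile.** Bring the synopsis and section 9.1 into agreement on dermoscopy images.

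The cost is one field and one table. Care, the primary endpoint and the sample size do not change. The downside is imprecise stratum estimates, as the intervals above show. The field should be in place before enrolment, since dermatoscope use may not be reliably recoverable afterwards from the decision algorithm alone.
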